5.5.6 Follow-up of Adverse Events

All AEs occurring during or after the subject has discontinued the study are to be followed up until resolved or judged to be no longer clinically significant, or until they become chronic to the extent that they can be fully characterized by the investigator.

If after the protocol defined AE collection period [see Section 5.5.1 Definition of Adverse Events], an AE progresses to a SAE, or the investigator learns of any (S)AE including death, where he/she considers there is reasonable possibility it is related to the study drug treatment or study participation, the investigator must promptly notify the sponsor.

5.5.7 Special Situations

Certain Special Situations observed in association with the study drug(s), such as incorrect administration (e.g., wrong dose of study drug, comparator, or background therapy) are collected in the eCRF, as Protocol Deviation per [Section 8.1.6 Major Protocol Deviations] or may require special reporting, as described below. These Special Situations are not considered AEs, but do require to be communicated to Astellas as per the timelines defined below.

If a Special Situation is associated with, or results in, an AE, the AE is to be assessed separately from the Special Situation and captured as an AE in eCRF. If the AE meets the definition of a SAE, the SAE is to be reported as described in [Section 5.5.5 Reporting of Serious Adverse Events] and the details of the associated Special Situation are to be included in the clinical description on the SAE worksheet.

The Special Situations are:

- Pregnancy
- Medication Error, Overdose and "Off label use"
- Misuse/abuse
- Occupational exposure
- Suspected Drug-Drug interaction

5.5.7.1 Pregnancy

The investigator will attempt to collect pregnancy information on any female partner of a male subject who becomes pregnant during the study dosing period or within 90 days from the discontinuation of dosing and report the information to delegated CRO according to the timelines in [Section 5.5.5 Reporting of Serious Adverse Events] using the Pregnancy Reporting Form.

The expected date of delivery or expected date of the end of the pregnancy, last menstruation, estimated conception date, pregnancy result and neonatal data etc., should be included in this information.

While pregnancy itself is not considered to be an AE or SAE, any pregnancy complication or termination (including elective termination) of a pregnancy is to be reported for a female study subject as an AE in the eCRF or SAE per [Section 5.5.5 Reporting of Serious Adverse Events]. For (S)AEs experienced by a female partner of a male subject, (S)AEs are to be reported via the Pregnancy Reporting Form. Additional information regarding the outcome of a pregnancy when also categorized as an SAE is mentioned below:

- "Spontaneous abortion" includes miscarriage, abortion and missed abortion.
- Death of a newborn or infant within 1 month after birth is to be reported as an SAE regardless of its relationship with the study drug.
- If an infant who dies more than 1 month after the birth, is to be reported if a relationship between the death and intrauterine exposure to the study drug is judged as "possible" by the investigator.
- Congenital anomaly (including anomaly in miscarried fetus)

Unless a congenital anomaly is identified prior to spontaneous abortion or miscarriage, the embryo or fetus should be assessed for congenital defects by visual examination. (S)AEs experienced by the newborn/infant should be reported via the Pregnancy Reporting Form. Generally, follow-up will be no longer than 6 to 8 weeks following the estimated delivery date.

5.5.7.2 Medication Error, Overdose and "Off-Label Use"

If a Medication Error, Overdose or "Off label Use" (i.e. use outside of what is stated in the protocol) is suspected, refer to [Section 8.1.6 Major Protocol Deviations]. Any associated (S)AEs are to be reported in the eCRF. If the AE meets the definition of a SAE, the SAE is also to be reported as described in [Section 5.5.5 Reporting of Serious Adverse Events] together with the details of the medication error, overdose or "Off-Label Use".

An overdose is defined as any dose greater than the protocol specified dose of enzalutamide 160 mg once daily. In the event of an enzalutamide overdose, the study drug should be stopped and subject should receive supportive care and monitoring. The Medical Monitor should be contacted.

Neither the effects of overdose of enzalutamide or an antidote to overdose are known. Subjects may be at increased risk of seizures following an overdose of enzalutamide.

5.5.7.3 Misuse/Abuse

If misuse or abuse of the study drug(s) is suspected, the investigator must forward the Special Situation worksheet to delegated CRO by fax or email immediately (within 24 hours of awareness). Any associated (S)AEs are to be reported in the eCRF. If the AE meets the definition of a SAE, the SAE is also to be reported as described in [Section 5.5.5 Reporting of Serious Adverse Events] together with details of the misuse or abuse of the study drug(s).

5.5.7.4 Occupational Exposure

If occupational exposure (e.g. inadvertent exposure to the study drug(s) of site staff whilst preparing it for administration to the patient) to the study drug(s) occurs, the investigator 31 May 2018 Astellas Page 42 of 61 Version 1.0

must forward the Special Situation worksheet to delegated CRO by fax or email immediately (within 24 hours of awareness). Any associated (S)AEs occurring to the individual associated with or resulting from the Special Situation are to be reported on the Special Situations worksheet.

5.5.7.5 Suspected Drug-Drug Interaction

If a suspected drug-drug interaction associated with the study drug(s) is suspected, the investigator must forward the Special Situation worksheet to delegated CRO by fax or email immediately (within 24 hours of awareness). Any associated (S)AEs are to be reported in the eCRF. If the AE meets the definition of a SAE, the SAE is also to be reported as described in [Section 5.5.5 Reporting of Serious Adverse Events] together with details of the suspected drug-drug interaction.

5.5.8 Supply of New Information Affecting the Conduct of the Study

When new information becomes available necessary for conducting the clinical study properly, the sponsor will inform all investigators involved in the clinical study as well as the regulatory authorities. Investigators should inform the IRB/IEC of such information when needed.

The investigator will also inform the subjects, who will be required to sign an updated informed consent form in order to continue in the clinical study.

5.6 Test Drug Concentration

Not applicable

5.7 Other Measurements, Assessments or Methods

Not applicable

5.8 Total Amount of Blood

The total amount of blood to be drawn for a subject will vary depending on the course of their disease and their duration on study treatment. At any time during the study, if laboratory values are determined to be abnormal, additional blood samples may be required for monitoring subject safety. The maximum amount of blood estimated to be collected from screening visit through day 169/week 25 visit is approximately 50 mL.

6 DISCONTINUATION

6.1 **Discontinuation of Individual Subject(s)**

The subject is free to withdraw from the study treatment and/or study for any reason and at any time without giving reason for doing so and without penalty or prejudice. The Investigator is also free to terminate a subject's involvement in the study at any time if the subject's clinical condition warrants it.

Discontinuation Criteria from Study Drug Treatment for Individual Subjects:

- Any AE that is intolerable to the subject which cannot be ameliorated by the use of adequate medical intervention and/or dose reduction or that in the opinion of the Investigator would lead to undue risk to the subject if dosing is continued.
- Subject who experiences a seizure or any condition that significantly predisposes the subject to seizure such as brain metastasis or clinically evident stroke.
- Subject who experiences a confirmed event of PRES by brain imaging, preferably by MRI.
- Subject initiates an investigational agent or new therapy for prostate cancer.
- Subject who has evidence of radiological disease progression and/or PSA progression as confirmed by the Investigator and is no longer deriving clinical benefit. Imaging test can be done at the discretion of the investigator and are not part of the study.
- Subject has discontinued ADT (GnRH agonist/antagonist) and has a testosterone value in the noncastrate range (> 50 ng/dL).
- Subject who is, in the opinion of the Investigator or the Medical Monitor, non-compliant with the protocol requirements.
- Subject is lost to follow-up despite reasonable efforts by the Investigator to locate the subject.
- Subject withdraws consent for the study.

Subject will be discontinued from the 30 day study follow-up (Safety or Long-term Follow-up) if any of the following occur:

- Subject is lost to follow-up despite reasonable efforts by the Investigator to locate the subject.
- Subject withdraws consent for further follow-up.
- Death.
- Study termination by the Sponsor.

6.2 Discontinuation of the Site

If an investigator intends to discontinue participation in the study, the investigator must immediately inform the sponsor.

6.3 Discontinuation of the Study

The sponsor may terminate this study prematurely, either in its entirety or at any study site, for reasonable cause provided that written notice is submitted in advance of the intended termination. Advance notice is not required if the study is stopped due to safety concerns. If the sponsor terminates the study for safety reasons, the sponsor will immediately notify the investigator and subsequently provide written instructions for study termination.

7 STATISTICAL METHODOLOGY

A Statistical Analysis Plan (SAP) will be written to provide details of the analysis, along with specifications for tables, listings and figures to be produced. The SAP will be finalized before the database hard lock at the latest. Any changes from the analyses planned in SAP will be justified in the Clinical Study Report (CSR).

In general, continuous data will be summarized with descriptive statistics (number of subjects, mean, SD, minimum, median and maximum), and frequency and percentage for categorical data.

7.1 Sample Size

The sample size of 50 subjects is not based on a statistical power calculation.

7.2 Analysis Sets

Detailed criteria for analysis sets will be laid out in Classification Specifications and the allocation of subjects to analysis sets will be determined prior to database hard-lock.

7.2.1 Full Analysis Set (FAS)

The full analysis set will consist of all subjects who received at least one dose of study drug and have at least one post baseline measurement. This will be the primary analysis set for efficacy analyses.

7.2.2 Safety Analysis Set (SAF)

The SAF consists of all subjects who took at least 1 dose of study drug, and will be used for safety analyses.

For the statistical summary of the safety data, the safety analysis set (SAF) will be used.

7.3 Demographics and Baseline Characteristics

Demographics and baseline characteristics will be summarized for the FAS and SAF.

7.3.1 Subject Disposition

The number and percentage of subjects who completed and discontinued treatment and reasons for treatment discontinuation will be presented. Similar tables for screening disposition, investigational period disposition and follow-up disposition will also be presented. All disposition details and dates of first and last evaluations for each subject will be listed.

7.3.2 Previous and Concomitant Medications

All previous and concomitant medications will be presented in a listing.

7.3.3 Medical History

Medical history for each subject will be presented in a listing.

7.4 Analysis of Efficacy

Efficacy analysis will be conducted on the FAS.

PSA response \geq 50% will be calculated for subjects with PSA values at the baseline assessment and at least 1 post-baseline assessment.

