5.3 Efficacy and Pharmacokinetics Assessments

5.3.1 Efficacy Assessments

PSA response \geq 50% is defined as \geq 50% reductions in PSA level from baseline to the lowest post-baseline PSA result as determined by the central laboratory, with a consecutive assessment conducted at least 3 weeks later to confirm the PSA response.

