1 INTRODUCTION

This Statistical Analysis Plan (SAP) contains a more technical and detailed elaboration of the principal features of the analysis described in the protocol, and includes detailed procedures for executing the statistical analysis of the primary and secondary endpoints and other data.

The SAP is finalized and signed prior to database hard lock.

This statistical analysis is coordinated by the responsible biostatistician of Data Science, API. Any changes from the analyses planned in the SAP will be justified in the Clinical Study Report (CSR).

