5 ANALYSIS SETS

In accordance with International Conference on Harmonization (ICH) recommendations in guidelines E3 and E9, the following analysis sets will be used for the analyses.

Detailed criteria for analysis sets will be laid out in Classification Specifications and the allocation of subjects to analysis sets will be determined prior to database hard-lock.

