5.1 Full Analysis Set (FAS)

The FAS will consist of all subjects who received at least one dose of study drug and have at least one post baseline measurement. This will be the primary analysis set for efficacy analyses.

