7.4 Analysis of Efficacy

Efficacy analysis will be conducted on the FAS.

PSA response rate (the proportion of patients with $\geq 50\%$ decline in PSA from baseline) will be summarized at each visit (See Section 7.11.3).

Confirmed PSA response rate (the proportion of patients with $\geq 50\%$ decline in PSA from baseline to the lowest postbaseline PSA result, with a consecutive assessment conducted at least 3 weeks later to confirm the PSA response) will be summarized.

Summary statistics of measured values and the percent changes from baseline will be calculated at each visit and mean \pm standard deviation (SD) plots will be constructed.

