7.11 Handling of Missing Data, Outliers, Visit Windows, and Other Information

7.11.1 Missing Data

As a general principle, missing data will not be imputed, except for the following exceptions.

The partial missing start/end dates of AE (Adverse Events), CM (Prior and Concomitant Prostate Cancer Medications, Concomitant Medications, Non-Medication Therapy), MH (Medical History, Primary Diagnosis), and PR (Radiation for Prostate Cancer, Procedures for Prostate Cancer) will be imputed as below.

- If the start day and/or month is unknown, the day and/or month will be imputed by 1st and January, respectively. In case of AE with onset after first dose of study drug, use the imputed date or the first dose date of study drug, whichever is later.
- If the end day and/or month is unknown, the day and/or month will be imputed by the last day of the month and December, respectively.

The imputed dates will be used to determine duration of disease at screening (See Section 6.3).

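### The confirmed PSA response rate leaves out dosed subjects without PSA, SAP 7.4 names no by-visit denominator, and a permitted early Safety Follow-up visit can miss every by-visit row

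*Protocol*

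**What the plan says.** **Analysis set.** Protocol 7.2.1 and SAP 5.1 define the FAS in the same way: "all subjects who received at least one dose of study drug and have at least one post baseline measurement". Neither says that the measurement must be PSA. SAP 5 adds that "Detailed criteria for analysis sets will be laid out in Classification Specifications".

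**Overall rate.** Protocol 7.4 places efficacy on the FAS and then narrows it: PSA response "will be calculated for subjects with PSA values at the baseline assessment and at least 1 post-baseline assessment". SAP 7.4 also uses the FAS but does not repeat the PSA condition. The SAP introduction describes the document as "a more technical and detailed elaboration of the principal features of the analysis described in the protocol". A response counts as confirmed "with a consecutive assessment conducted at least 3 weeks later to confirm the PSA response" (Protocol 5.3.1; SAP 6.1 is equivalent).

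**By-visit rate.** SAP 7.4 also plans a response rate at each visit and refers to 7.11.3. That section decides which value represents a visit, not who is in the denominator. SAP 7.1 drops a subject with no baseline value from change-from-baseline calculations. SAP 7.11.1 says "As a general principle, missing data will not be imputed, except for the following exceptions", and those exceptions are partial dates.

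**Safety Follow-up.** Protocol 2.2.1, the Table 1 footnote and SAP 3.2 place this visit 30 days after last dose, or before new prostate cancer therapy if that comes first. The SAP 7.11.3 table accepts 30 ± 7 days after last dose only. For discontinued subjects, the Day rows accept values up to the withdrawal day.

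**The concern.** In a single-arm study the percentage is itself the efficacy result. A dosed subject with no PSA after baseline cannot be a responder, but under Protocol 7.4 he is not a non-responder either: he leaves the denominator. Any such omission moves the rate in one direction only. Counting him as a non-response gives a rate that is free of this selection, although not every such subject is a treatment failure.

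The by-visit rate raises a related question of labelling. The analysis visits run to Day 1429, and subjects stop treatment for reasons that include progression with loss of benefit (Protocol 6.1). A late-visit percentage cannot be read without knowing how many subjects it rests on.

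The Safety Follow-up window is a separate matter. The design permits a visit that the analysis window does not recognise, so its vital signs, laboratory and PSA values can drop out of the by-visit tables.

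**Working it through.** The documents state no response rate or dropout rate, and the sample size of 50 is declared not to rest on a power calculation. There is therefore no planned figure to reproduce. The numbers of responders and of omitted subjects below are assumptions.

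**1. Direction.** Let D be subjects dosed, k the dosed subjects left out under Protocol 7.4, and R the confirmed responders.

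- A confirmed responder must have a baseline and a post-baseline PSA, so R is the same under both denominators.
- Planned rate = R/(D − k); all-dosed rate = R/D.
- Their ratio is D/(D − k) ≥ 1, with equal rates only if k = 0 or R = 0.

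**2. Size, with D = 50.**

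| R (assumed) | All dosed | k = 1 | k = 2 |
|---|---|---|---|
| 15 | 15/50 = 30.0% | 15/49 = 30.6% (+0.6) | 15/48 = 31.3% (+1.3) |
| 25 | 25/50 = 50.0% | 25/49 = 51.0% (+1.0) | 25/48 = 52.1% (+2.1) |
| 35 | 35/50 = 70.0% | 35/49 = 71.4% (+1.4) | 35/48 = 72.9% (+2.9) |

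For scale, the exact (Clopper-Pearson) 95% interval for 25/50 is 35.5% to 64.5%, about ±14.5 points.

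**3. How large k might be.** Baseline PSA has two scheduled occasions, Screening and Day 1, and SAP 7.1 takes the latest available pre-dose value. Post-baseline PSA is scheduled at each on-drug visit from Day 29 and at Safety Follow-up. Entry requires an estimated life expectancy of at least 6 months. A k of 0 to 2 is therefore a reasonable working range, though no document gives it.

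**4. By-visit denominator.** The no-imputation rule in SAP 7.11.1 and the missing-baseline rule in SAP 7.1 both point to observed cases, but SAP 7.4 does not say so. As an assumed illustration, 27 responders among 45 subjects with PSA and 9 among 15 are both 60.0% of those observed. Against 50 dosed they are 27/50 = 54.0% and 9/50 = 18.0%. The two denominators answer different questions, so the reader needs n at each visit.

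**5. Safety Follow-up window.** 30 − 7 = day 23 and 30 + 7 = day 37 after last dose.

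| Timing of the value | By-visit row under SAP 7.11.3 |
|---|---|
| 23 to 37 days after last dose | Safety Follow-up |
| Before day 23, on or before withdrawal day | A Day row, if within 7 days of a specified day |
| Before day 23, after withdrawal day | None |

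The last line is the gap. The documents do not define withdrawal day, so how often it would arise cannot be determined.

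**The case against.** The strongest reply is that any evaluable-subject rate has this property. Protocol 7.4 states its restriction openly, for a secondary endpoint with no test attached, and counting missing as non-response is one convention among several. SAP 7.2.1 already reports how many took study drug and who was excluded from the FAS, with reasons. Only FAS subjects lacking PSA would go uncounted. All of this stands. It limits the point to a supplementary rate and clearer labels.

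Four stronger readings are tempting, and the documents do not support them.

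- *The headline rate is materially inflated.* Five omitted subjects would turn 25/50 into 25/45 = 55.6%, but nothing in the PSA schedule suggests five.
- *The SAP contradicts the protocol, or leaves by-visit missing data open.* The SAP presents itself as elaborating the protocol, so leaving out the PSA condition is not a conflict. SAP 7.1 and 7.11.1 indicate observed cases. Denominators may also be settled in the Classification Specifications or the table specifications, which are not among these documents.
- *Each visit's rate should be set against all treated subjects not yet administratively cut off.* The documents define no such group. Counting everyone off treatment as a non-responder at late visits mixes staying on treatment with PSA response.
- *Values after withdrawal are lost.* Those taken 23 to 37 days after last dose have the Safety Follow-up row. An early visit that misses every row still appears in the listings. The windows do not bar it from the study-day plots or the highest-value liver summaries. It can also still count toward confirmed response, whose definition cites no visit window.

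**Conclusion.** The point holds in a limited form. The Protocol 7.4 rate equals or exceeds confirmed responders over all dosed subjects. That direction is certain. The size is an assumption: zero if every dosed subject has the required PSA, and 1.0 to 2.1 points with 25 responders of 50 dosed and one or two left out. That is well inside the sampling error, but it always goes the same way. No hypothesis test, error rate or power is involved.

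The missing by-visit denominator is a labelling gap, since the SAP's general rules already lean to observed cases. The Safety Follow-up mismatch is a real inconsistency between design and analysis window, and its effect is confined to the by-visit tables. Overall this is an inexpensive improvement, between optional and recommended.

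**What to change.** 1. In SAP 7.4, add the confirmed PSA response rate over all dosed subjects (the safety analysis set), counting no evaluable PSA or no confirmatory PSA as non-response. Show it beside the Protocol 7.4 rate, with the number of dosed subjects left out of the latter.
2. In SAP 7.4, label the by-visit rate as observed cases. At each visit print the number with PSA beside the number dosed. No further comparator is needed.
3. In SAP 7.11.3, assign the Safety Follow-up record by visit label, so that a permitted early visit keeps its row.

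This takes a few sentences and some extra columns. It needs no new data and removes no planned result. The all-dosed rate goes beyond the efficacy set in Protocol 7.2.1 and 7.4, so it should be covered by an amendment or justified in the clinical study report. The downside is a slightly lower figure beside the planned one, in which a subject whose confirmatory sample is missing counts as a non-responder.
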